STUDY ASSESSMENTS AND PROCEDURES	Patients will be assessed in the emergency department by the investigator and/or study staff for signs and symptoms of worsening HF due to congestion or fluid overload. If it is determined by the investigator that the patient requires parenteral diuresis or continued diuresis outside of the ED care setting, and meets all study eligibility criteria, he/she may be consented and enrolled into the study.

	
The treatment comprises a 5-hour subcutaneous infusion of Furoscix via the Furoscix Infusor. Subjects will be instructed on the use of the Furoscix Infusor by the investigator and/or study staff in accordance with the instructions for use. The initial dose of the study product may be administered on the day of enrollment. Some subjects may not require their initial dose until the next day. Doses will be provided to the subject for self-administration or administration by a caregiver in the home setting as directed by the investigator or study staff. No more than 7 doses of Furoscix are permitted during the 30-day study period. If a subject uses the allotted 7 doses and additional doses are required to control signs and symptoms of congestion when oral diuretics are not effective, approval by the medical monitor is required. Subjects will receive scheduled at-home telephone calls from a HF nurse, or designee, on Days 1 and 7, and one call between Days 14-21. Unscheduled calls can be conducted as needed. Planned in-clinic visits will be conducted between Day 2-4 and then Day 30±3 days. Unscheduled at-home telephone calls by an HF nurse, or designee, and unscheduled in-clinic visits may be performed if felt clinically indicated by the study team or the clinical provider.
 
The study period will be up to 30 days after enrollment. All outcomes will be assessed up to 30 days after the initial discharge from the emergency department.

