1.1.3. Risk Management

Subjects will be trained by the study staff on appropriate use of the Furoscix Infusor and will receive specific instructions and study materials created for the study (based on the Furoscix Infusor Instructions for Use) that include information regarding what to do in case of certain events during the drug delivery period.

Subjects should be transitioned back to their oral maintenance diuretic regimen when clinically indicated at the discretion of the investigator (approximately 4 doses). After Subjects have been transitioned to their oral maintenance diuretic regimen, additional doses of Furoscix can be prescribed during the 30-day study period as needed based on the presence of clinical triggers (dyspnea on exertion, edema, and/or excess weight gain) as determined by the investigator. No more than 7 doses of Furoscix is permitted during the 30-day study period. Additional doses beyond 7 requires approval by the medical monitor.

Subjects will receive scheduled at-home telephone calls from a HF nurse, or designee, on Days 1 and 7, and one call between Days 14-21. Unscheduled calls can be conducted as needed. The primary purpose of the calls will be to evaluate the safety and efficacy of diuresis and the need to adjust diuretic therapy. Two planned in-clinic visits will be conducted: the first occurring within Days 2-4 and the second occurring on Day 30 ± 3 days. These visits will include laboratory testing of creatine and electrolytes.

Unscheduled at-home telephone calls by an HF nurse, or designee, and unscheduled in-clinic visits may be performed if felt clinically indicated by the study team or the clinical provider.

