3. INVESTIGATIONAL PLAN

3.1. Overall Study Design and Plan

This adaptive clinical trial will include a prospective treatment arm (i.e., Furoscix administered via the Furoscix Infusor) administered outside the hospital that will be compared to a propensity-matched historical control arm consisting of patients admitted to the hospital for ≤ 72 hours (i.e., TAU). This healthcare cost data from the control arm will be generated from administrative claims data. Eligible patients for the Furoscix arm will be patients with worsening HF due to congestion who initially present to the emergency department and who are expected to require parenteral diuresis. The decision as to whether a patient will be enrolled in the study to receive Furoscix will be made collaboratively by an emergency medicine physician and a heart failure specialist or cardiologist.

The control arm will be populated with claims data for patients who presented to the emergency department for worsening HF and are admitted to the hospital for ≤ 72 hours for the treatment of HF. The filter will be further strengthened by analyzing diagnostic codes and resource utilization during their hospital stay to remove patients with renal failure or those that were in the hospital for other reasons. Furoscix-treated patients will be matched to

controls from an administrative claims database in ratios ranging from 1:1 to 4:1 using methods reported by Millar and Pasta 2010.¹ The simulations will be used to find the matching ratio at which the level of precision is optimized without biasing the variance of the outcome measure. Additional methodological details are described in the prespecified statistical analysis plan.

Patients presenting to the emergency department with worsening HF and meeting all study eligibility criteria may be consented and enrolled in the study to receive diuresis outside of the hospital setting with Furoscix.

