6.2.5. Days 14 – 21 (Telephone Call Follow-Up)

Telephone call follow-ups will be conducted by an HF nurse, or designee, as deemed necessary by the investigator between Days 14-21. The primary purpose of these calls will be to assess whether the subject has experienced or is experiencing a study related adverse event, to assess status of change back to oral medication, and to assess congestion.

The suggested script for conducting these telephone calls is the same that is described previously and will include:

- Suggested Telephone Script
- Additions or discontinuations of concomitant medications as per section 5.7 (record on concomitant medication form)
- Assessment for adverse events
- Assessment for interval hospitalizations, emergency department visits, or unscheduled clinic visits
 - Been admitted to the hospital
 - Been admitted to the hospital for HF-related issues
 - Been seen at the emergency department for HF-related issues
 - Been seen in an outpatient clinic (including immediate care clinic) for HF-related issues
 - Sought any additional or new medical treatment for HF-related issues
- Device start and stop time for each dose (if received study drug after Day 2-4 clinic visit)
- Problems with drug or device use (if received study drug after Day 2-4 clinic visit)

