6.2.7. Unscheduled Telephone Calls and Clinic Visits

There are two forms of unscheduled follow-ups specified in this protocol: telephone call and clinic visit. These may be assigned at any time at the discretion of the investigator and may arise from a request by the subject or caregiver, a request by the HF nurse, or designee, conducting telephone follow-ups, or by the judgement of the investigator. Note that the investigator can pre-specify at any time the number and timing of unscheduled follow-up visits.

If subjects experience worsening signs and symptoms they can be seen in the clinic as an unscheduled visit. For subjects presenting for an unscheduled visit the following assessments will be performed:

- Cardiopulmonary Exam including NYHA Classification
- Vital Signs
- Weight
- Labs drawn at the discretion of the investigator (including BNP or NT-proBNP)
- Assess for adverse events

All subjects will have the option to receive unscheduled phone call by an HF nurse, or designee, at any time following the initial discharge from the emergency department. The primary purpose is to respond to issues affecting proper use and administration of the Furoscix Infusor. While these calls will follow according to the aforementioned script, the HF nurse, or designee, will address - per his or her best professional judgement - specific issues reported by the patient or caregiver.

Additionally, the HF nurse, or designee, will ask (and document the responses) whether the subject has since the previous follow-up:

- Been admitted to the hospital
- Been admitted to the hospital for HF-related issues
- Been seen at the emergency department for HF-related issues
- Been seen in an outpatient clinic (including immediate care clinic) for HF-related issues
- Sought any additional or new medical treatment for HF-related issues

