3.5.3.1. Healthcare Resource Utilization (HCRU) and Costs

For each patient in the historical control and prospective arm, 30-day follow-up HF-related and all-cause healthcare resource utilization (HCRU) will be estimated and reported.

For cost inputs, events that are major contributors of the costs will be included in the analysis, including any visits and hospitalizations that are either HF-related or all-cause. Using the dataset created for matching, cost benchmarks for each event (HF-related and all-cause) i.e. mean and standard deviation will be derived. For each patient in the historical and prospective cohorts, 30-day HF-related and overall costs will be estimated by summation of applied cost benchmarks to each resource utilization event observed during the 30-day period starting from the beginning of HF-worsening episode.

Overall cost of care will include cost attribute to all-cause HCRU. Total HF-related medical costs will be comprised of the hospitalization costs and outpatient visits costs attributable to HF-related HCRU (defined by claims with a primary diagnosis of HF). All costs will be inflated to \$2019 using Medical Care Consumer Price Index (CPI). All costs included will be gross costs including payer and patient costs.

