3.5.4. Step 3: Compute Boundary Values for Primary Outcome

Boundary values for the primary outcome will be derived via the SEQDESIGN (REF SAS SEQDESIGN) procedure in SAS; specifically using a two-sided O’Brien Fleming design which has conservative stopping boundary values at early stages, and boundary values at the final stage that are close to the fixed-sample design. This produces a conservative design because compared to other approaches, the O’Brien-Fleming approach makes it more difficult to reject the null hypothesis in early stages than in later stages (null hypothesis being that there is no difference in 30-day HF-related direct medical costs between the Furoscix Infusor and historical control arms).

Assume that the total 30-day HF-related direct medical costs are normally distributed with means μ_e and μ_c for individuals in the Furoscix Infusor and historical control groups, respectively. The null hypothesis of no effect for the Furoscix Infusor is $H_0 : \theta = 0$, where $\theta = \mu_e - \mu_c$

The specific procedure for determining the boundary values for the primary outcome are specified elsewhere (REF SAS SEQDESIGN). Utilizing this procedure requires that we prespecify the meaningful difference between groups and the standard deviation thereof in order to achieve the specified power. The boundary values will be estimated based on a difference of \$2,100 (based an average hospital cost of a patient hospitalized for ≤ 72 hours with a primary diagnosis of HF (Diagnosis Related Group Code 291, 292 and 293) of \$8,600 (standard deviation: \$3,045), 68 patients (34 in each group) are required to have an 80% chance of detecting a decrease in hospital costs to \$6,500 at a significance level of 5%).

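### The SAP cost rule sets no price for the HF-nurse calls that the protocol adds to the Furoscix arm, so the saving omits a direct cost and belongs to the Infusor with telephone follow-up, not the Infusor alone

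*Protocol*

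**What the plan says.** **The calls.** The protocol Synopsis (Study Assessments and Procedures) states: "Subjects will receive scheduled at-home telephone calls from a HF nurse, or designee, on Days 1 and 7, and one call between Days 14-21". Sections 1.1.3 and 6.2 repeat this schedule. Section 1.1.3 gives the aim: "The primary purpose of the calls will be to evaluate the safety and efficacy of diuresis and the need to adjust diuretic therapy". Section 6.2.3 says the same of the Day 1 and Day 7 calls.

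Section 6.2.5 differs on the third contact: "Telephone call follow-ups will be conducted by an HF nurse, or designee, as deemed necessary by the investigator between Days 14-21". It lists study-related adverse events among the purposes and continues: "to assess status of change back to oral medication, and to assess congestion". Adjusting diuretics is not named there. Section 6.2.7 adds: "All subjects will have the option to receive unscheduled phone call by an HF nurse, or designee, at any time". Those unscheduled calls are mainly for problems in using the Infusor.

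**The controls.** Protocol 3.1: "This healthcare cost data from the control arm will be generated from administrative claims data". Neither document describes study follow-up for controls or says what calls they had in routine care.

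**The cost rule.** SAP 3.5.3.1 applies benchmarks from the matching dataset to each resource-use event, naming visits and hospitalizations as the main contributors. For the HF-related part: "Total HF-related medical costs will be comprised of the hospitalization costs and outpatient visits costs attributable to HF-related HCRU". No benchmark or unit price for a nurse call appears. Protocol 6.1.1 is wider: it takes in every direct medical cost attributable to resource use.

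**The hypothesis.** SAP 3.3.5 frames the null as no cost difference between the two arms. SAP 3.5.4 words it as a product effect: "The null hypothesis of no effect for the Furoscix Infusor is" θ = 0.

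**The concern.** The trial's purpose is economic. One arm receives extra contacts with a clinical purpose, and the rule that turns resource use into dollars does not price them. Two things follow.

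First, if SAP 3.5.3.1 is followed as written, the Furoscix arm's 30-day cost excludes care that the protocol itself supplies. Leaving out a positive cost in that arm makes the reported saving larger than it would be with the calls charged.

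Second, the calls start after the ED visit. The propensity model uses variables defined at enrollment or the index date, so it cannot balance follow-up given later to one arm. Whatever the calls do to later admissions or visits is part of the measured difference, and no planned analysis isolates it. A payer reading a result for the Infusor would not know that it was obtained with a nurse-call programme attached.

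**Working it through.** **Step 1. Reproduce the plan's own figure.** Inputs from protocol 8.1 and SAP 3.5.2: means $8,600 and $6,500, SD $3,045, 80% power, 5% level. SAP 3.3.3 makes the test two-sided.

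- Planning difference: $8,600 − $6,500 = $2,100.
- n per group = 2 × [SD × (1.960 + 0.842) / difference]² = 2 × [3,045 × 2.802 / 2,100]² = 33.005, rounded up to 34.
- The two-sample t-test solution is 33.99, also 34.

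The stated 34 per group (68 in all) is reproduced. Normal-approximation power at 34 per group is 81.2%.

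**Step 2. Count the calls.** The Synopsis and sections 1.1.3 and 6.2 give three scheduled calls. Section 6.2.5 makes the last one discretionary, which leaves two certain. On-demand calls have no stated limit.

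**Step 3. Direct cost left out.** The documents give no price per call; $20-$150 is an assumed range. Charge = calls × price; share = charge / $2,100.

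| Price per call (assumed) | Two calls | Share | Three calls | Share |
|---|---|---|---|---|
| $20 | $40 | 1.9% | $60 | 2.9% |
| $50 | $100 | 4.8% | $150 | 7.1% |
| $100 | $200 | 9.5% | $300 | 14.3% |
| $150 | $300 | 14.3% | $450 | 21.4% |

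Each on-demand call adds $20-$150, or 1.0-7.1% of $2,100 (20/2,100 and 150/2,100). Three calls would cancel the whole planning difference only at $2,100 / 3 = $700 each, far above the assumed range.

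**Step 4. Effect on power.** Suppose $2,100 is the difference before calls are charged. The same charge for every Furoscix subject moves the mean and leaves the SD alone.

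| Three calls at (assumed) | Net difference | n per group for 80% | Power at 34 per group |
|---|---|---|---|
| not charged | $2,100 | 34 | 81.2% |
| $20 | $2,040 | 35 | 78.9% |
| $50 | $1,950 | 39 | 75.2% |
| $150 | $1,650 | 54 | 60.8% |

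**Step 5. Indirect effect.** The documents give no information on how the calls change utilization. For scale only, take the $8,600 planning figure as the price of an admission. A change of 1, 5 or 10 admissions per 100 subjects is then worth $86, $430 or $860 per subject (4.1%, 20.5% or 41.0% of $2,100). The sign is open: a call may avert an admission, and under section 6.2.7 a request from the nurse making the calls may also lead to an unscheduled visit.

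**The case against.** The case on the other side has real substance.

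- **The rule is not a closed list.** SAP 3.5.3.1 introduces visits and hospitalizations as inclusions, and the schedules of assessments label the telephone contact a visit. The claims codebook and the CRF are not reproduced in the text. An analyst could price the calls. This stands as a caution, but no benchmark is given, the unit prices come from claims, and the choice would remain open until the data are in hand.
- **Calls are priced in neither arm.** Controls may have had routine calls, which the rule does not price either. This stands: only the absence of a study programme is documented, so charging one arm is debatable as the primary analysis.
- **The calls also gather trial data** (diary, infusion times, adverse events), so part of their cost is arguably research. This stands too, and is a second reason to place the charge in a sensitivity analysis.
- **The stated purpose is already a strategy comparison**, about avoiding hospital care. That is true of the background sections and of SAP 3.3.5. The primary endpoint and SAP 3.5.4 still name only the Infusor.

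A reader might go further and infer that the calls prevent readmissions, so that both omissions inflate the saving, or that the saving would disappear without them. The documents do not support this. The effect on utilization has no stated size or direction. Under SAP 3.5.3.1 the 30 days run from the start of the worsening episode, so the control's index admission, the cost on which the planning difference is based, falls inside the window. Furoscix subjects have left the ED before the first scheduled call, so the calls cannot create that part of the contrast.

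**Conclusion.** The point holds in a limited form and is worth correcting. The Furoscix arm receives two or three scheduled nurse calls plus on-demand calls, the Day 1 and 7 calls have a stated treatment purpose, and the cost rule as written does not charge them. For three calls the omitted cost is $60-$450 per subject, or 3-21% of $2,100; at $50 per call it is $150, or 7%. These figures rest wholly on an assumed $20-$150 per call and on $2,100 as the yardstick. Within that range the charge reduces the planned saving without removing it.

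The indirect effect of the calls cannot be sized or signed from the documents. What is established is that the design cannot separate it from the product, so the measured difference belongs to the combined strategy. It should not be read that controls had no calls, or that every Furoscix subject is certain to have three.

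**What to change.** 1. **SAP 3.5.3.1.** Prespecify a sensitivity analysis of 30-day HF-related and overall cost that adds a fixed unit price, with its source and in the SAP's 2019 dollars, for each scheduled and unscheduled nurse call in the Furoscix arm. Report it beside the result without the charge. State that calls to controls are not observable in claims.
2. **Primary endpoint and SAP 3.3.5 and 3.5.4.** Describe the comparison as the Furoscix Infusor with protocol nurse telephone follow-up versus treatment as usual, and limit the conclusion to that strategy.
3. **Protocol.** Reconcile section 6.2.5 with the Synopsis and sections 1.1.3 and 6.2 on whether the Day 14-21 call is scheduled or discretionary, since the number of calls charged depends on it.

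The cost is wording in both documents, one sourced price, and a check that the CRF counts every call. The downside is a slightly less favourable saving in the sensitivity analysis and a narrower claim.

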1. INTRODUCTION AND RATIONALE

Heart failure (HF) affects 6.5 million adults in the United States, a figure that is expected to grow to 8 million by 2030. In the United States, HF is implicated as the cause of at least 1-2 million hospitalizations and 700,000 emergency department visits annually, and HF admissions generate the highest number of 30-day readmissions among Medicare enrollees. It is also estimated that 90% of patients presenting to the Emergency Department with worsening HF are admitted to the hospital and approximately 50% of hospital admissions for HF admitted from the emergency department could potentially be avoided.

Intravenous furosemide is commonly indicated for the management edema which is commonly present in worsening HF as the absolute bioavailability of oral furosemide is low, highly variable and is exacerbated during an acute event. Recognizing this limitation of oral furosemide, national and international guidelines recommend that patients should be administered intravenous diuretics when significant signs and symptoms of volume overload are present. Thus, hospital admission or utilization of an observational unit is generally required. Admitting patients to the hospital, solely for the administration of intravenous furosemide, is expensive and increases risks of hospital-associated morbidity and mortality. Alternative treatment paradigms that shift HF management outside of the hospital are needed.

Approximately 60% of hospital admissions in patients with HF are due to sodium retention and volume overload. While subcutaneous administration of furosemide would enable diuresis as an outpatient, avoiding a hospital admission, the current commercially available furosemide injectable products have an alkaline pH and poor solubility making them unsuitable for subcutaneous administration. A novel, pH neutral formulation of subcutaneous furosemide (Furoscix, Furosemide Injection 80 mg/10 mL for subcutaneous use) has been developed to minimize burning and discomfort with subcutaneous administration and is delivered via the Furoscix Infusor: a wearable, pre-programmed on-body subcutaneous delivery system.

Furoscix administered 80 mg subcutaneously via the Furoscix Infusor, with 30 mg administered over the first hour followed by 12.5 mg per hour over the subsequent four hours produced similar exposures of furosemide and equivalent diuresis and natriuresis compared to two bolus injections of furosemide 40 mg dosed over 2 minutes, two hours apart.

The purpose of this study is to evaluate the economic impact of hospital avoidance and safety with management of worsening HF due to congestion with Furoscix administered via the Furoscix Infusor outside the hospital setting in patients initially presenting to the emergency department.

1.1. Risk: Benefit Evaluation

1.1.1. Potential Benefits of Participating in the Study

The potential benefit to the participants beyond their contribution to the development and testing of this product is the potential avoidance of a hospital admission and administration of parenteral diuretics outside of the hospital setting.

1.1.2. Potential Risks of Participating in the Study

Furosemide has been extensively studied and used clinically for over 50 years. It is generally considered a safe and effective pharmaceutical product. Subjects may experience marked diuresis following the placement and activation of this drug-device combination product. Subjects should be instructed to have ready access to suitable toilet facilities. Marked diuresis may be accompanied by a drop in blood pressure including orthostatic hypotension and associated signs and symptoms.

